At the in-person interview, the study will be explained by one of the study team members. All study team members will be trained to obtain consent. The study will be explained in its entirety. Along with explaining each of the testing and evaluation procedures, the study team member will explain every possible risk that the participant may encounter. The potential participant will be told that there is a possibility that he or she will not be eligible if any of the exclusion criteria are found to be true (i.e. a screening failure). This is an investigational, observational study. As such, no direct permanent benefits will be expected.

Potential participants will be encouraged to ask questions throughout the process. Potential participants will be informed of their right to withdraw at any time and that choosing to not participate will not infringe on any of their regular VA benefits or medical care. Once he/she has no further questions and the study team is confident that the potential participant fully understands the protocol and its risks, then the participant will be asked whether he or she is willing to sign the ICF.

Procedures:

General: All procedures are performed in a seated position with elbows at roughly 90 degrees and hands resting on a pillow in pronated position. Electrophysiological measurements are made using the dominant or stronger affected arm. Safety (blood pressure, heart rate, pulse oxygenation, peak expiratory flow rate, and structured symptom questionnaire) and tolerability are closely monitored throughout all experiments (see Human Subjects section).

Electromyography (EMG): EMG is recorded using surface sensors with 300x preamplification, 15-2,000 Hz bandwidth, and internal grounding (Motion Lab Systems). EMG input is collected at a sample rate of 5,000 Hz via digital acquisition board and customized LabVIEW software (National Instruments). Muscles recorded may include abductor pollicis brevis (APB), abductor digiti minimi (ADM), first dorsal interosseous (FDI), flexor carpi radialis (FCR), extensor carpi radialis (ECR), and/or biceps brachii.

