Aim 1 data analysis: Peak-to-peak amplitude (or F-wave persistence) of conditioned pulses will be normalized to that of unconditioned pulses. For each interaction paradigm, repeated-measure analysis of variance (ANOVA) with factors of subject group, conditioning stimulus intensity, interstimulus interval, and muscle will be performed. Post hoc pairwise comparisons will be made using Tukey's method.

Aim 1 Timeline:

Each subject will undergo two testing sessions on separate days, with a minimum of 24 hours and a maximum of two weeks between visits. Per subject, Aim 1 participation would therefore take 2 to 15 days. 27 subjects will be enrolled, resulting in 54 total testing sessions. A very conservative projection of completing 1.5 testing sessions per week would result in a timeline of 36 weeks or 9 months for completing Aim 1, not including recruitment.

Aim 2: Determine optimal CES parameters for acutely facilitating concurrent arm and hand movements.

Volitional limb movements depend on the same corticospinal and spinal motor circuits as those activated by TMS and F-waves. Therefore, since preliminary data shows that subthreshold CES facilitates TMS responses, CES may also be able to facilitate volitional limb movements. The experiments in Aim 2 will shed light on this clinically applicable question.

Volitional motor tasks: Maximal voluntary effort will be defined as the largest response from 3 attempts prior to testing. Effort will be measured using a customized dynamometer or the root mean square (RMS) of electromyographic activity in the target muscles. The tasks are: thumb-third finger opposition (C8-T1 levels), or wrist extension by extending the dorsal hand laterally against a mounted load cell (C6 level). A combined finger opposition/wrist extension task will also be tested. Subjects will be instructed to perform tasks at target effort levels based on real-time display of ongoing EMG or force output.

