CES-motor task interaction: While performing volitional motor tasks at 100%, 50%, or 15-20% of maximal effort, conditioning CES (or sham) pulses will be delivered at a range of intensities between 30%-175% of resting motor threshold. For subthreshold CES, either single or "theta bursts" (3 pulses at 50 Hz)⁴⁸ will be delivered. The effect of CES pulses on RMS electromyographic activity over the subsequent 200 ms will be measured at several different arm and hand muscles and divided by the baseline RMS from the preceding 100 ms. At least 10 seconds will elapse between each CES/motor task combination. Effort level and CES pulse parameters will be varied in pseudorandom order, until 8 responses per parameter have been recorded.

Aim 2 Outcomes:

- Facilitation: At each muscle, the effect of CES pulses on RMS electromyographic activity over the subsequent 200 ms (in 25 ms bins) will be measured and normalized to the baseline RMS from the preceding 100 ms.
- Silent period: At each muscle, the duration of electromyographic silence is measured from the end of the CES-evoked potential until the resumption of volitional muscle activity (defined as mean rectified EMG amplitude less than or greater than mean baseline activity + 2 standard deviations⁸³, respectively).

Hypothesis 2.1: Subthreshold CES will *facilitate* concurrent wrist and hand muscle activation.

Hypothesis 2.2: High-intensity CES will transiently *inhibit* concurrent wrist and hand muscle activation.

Interpretation: Confirmation of Hypothesis 2.1 would substantiate the findings of Hypotheses 1.1 and 1.2 and our updated preliminary data that indicate CES's ability to positively modulate corticospinal and/or motor neuron excitability. We expect optimal facilitation when subthreshold CES is delivered at closer to motor threshold intensity. We do not know whether the effects will differ depending on intensity of volitional effort, but if so, further experiments could investigate the roles played by peripheral, spinal, and supraspinal components of effort intensity⁸⁴. Most importantly, confirmation of Hypothesis 2.1 would represent an

opportunity to directly translate and test this paradigm for lasting clinical benefit by combining repetitive subthreshold CES with repetitive task-oriented physical exercise training in a subsequent study.

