If high-intensity CES inhibits concurrent volitional activity as predicted by Hypothesis 2.2, this would be analogous to the 'cortical silent period' (CSP) noted when cortical TMS is delivered during volitional contraction^{7,8}. The early phase of CSP (the first 50-75 ms after onset of the cortical motor-evoked potential) is mediated by poorly understood spinal mechanisms⁷. Our observations of the onset and duration of a 'spinal silent period' (SSP) in response to CES would shed mechanistic light on this phenomenon.

Aim 2 Data analysis: Rather than peak-to-peak amplitude, the effects of CES on concurrent volitional muscle contraction will be measured using RMS. RMS in 25 ms bins over the 200 ms following each CES pulse will be normalized to the baseline RMS during the 100 ms prior to each pulse. Repeated-measure analysis of variance (ANOVA) with factors of subject group, volitional effort intensity, CES intensity, post-stimulus timebin, and muscle will be performed. Post hoc pairwise comparisons will be made using Tukey's method.

Aim 2 Timeline:

Each subject will undergo two testing sessions on separate days, with a minimum of 24 hours and a maximum of two weeks between visits. Per subject, Aim 2 participation would therefore take 2 to 15 days. 24 subjects will be enrolled, resulting in 48 total testing sessions. A very conservative projection of completing 1.5 testing sessions per week would result in a timeline of 32 weeks or 8 months for completing Aim 2, not including results processing/dissemination.

4. Possible RISKS and protective actions

For subjects with ALS, there is a risk of falling during transfers between different testing positions. To minimize this risk, a clinician will be at the participant's side at all times to assess comfort and provide manual assistance/stabilization as necessary.

The surface electromyography recording and stimulating electrodes and tape have adhesive backing. Therefore, minimal risks such as transient skin irritation at the sites of surface electrode application may occur. Areas with excessive hair will be shaved prior to adhesive application.

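### Aim 2's facilitation ratio and task-blind ANOVA mix a muscle's prime-mover data with its antagonist or resting data, so a rise need not mean that the movement was facilitated

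*Combined protocol and SAP*

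**What the plan says.** All references are to section 3 of the combined protocol and SAP unless stated.

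- **Aim.** The Aim 2 title is "Determine optimal CES parameters for acutely facilitating concurrent arm and hand movements".
- **Hypothesis.** Hypothesis 2.1 is narrower: subthreshold CES will facilitate "concurrent wrist and hand muscle activation". Section 1 words it as arm and hand muscles.
- **Outcome.** Under Aim 2 Outcomes: "Facilitation: At each muscle, the effect of CES pulses on RMS electromyographic activity over the subsequent 200 ms", in 25 ms bins. The CES-motor task interaction paragraph says that the effect "will be measured at several different arm and hand muscles and divided by the baseline RMS from the preceding 100 ms". Neither place sets a floor for that baseline.
- **Muscles.** The Electromyography paragraph gives a list of candidates, not a fixed set. Besides three hand muscles (APB, ADM, FDI) it names "flexor carpi radialis (FCR), extensor carpi radialis (ECR), and/or biceps brachii", so it holds both a wrist flexor and a wrist extensor.
- **Tasks.** Volitional motor tasks lists thumb-to-third-finger opposition, wrist extension against a load cell, and the two combined. Target muscles, the dynamometer and the load cell appear there only as means of measuring and displaying effort. No muscle is assigned to a task, and no force outcome is listed.
- **Model.** Under Aim 2 Data analysis, the ANOVA factors are subject group, effort, CES intensity, "post-stimulus timebin, and muscle will be performed". Motor task is not among them.
- **Use of the result.** The Interpretation paragraph treats confirmation of Hypothesis 2.1 chiefly as the ground for a later study combining CES with exercise training.

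**The concern.** The same muscle plays different parts in different tasks. ECR drives wrist extension but is not the prime mover of finger opposition; FCR opposes wrist extension. With muscle in the model and task left out, all of a muscle's trials feed one factor level whatever it was doing, and Tukey comparisons on that factor cannot recover the distinction.

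The ratio adds a second difficulty. Dividing by a muscle's own pre-pulse RMS gives a stable scale when the muscle is contracting. When it is near rest the denominator is small, and a trivial absolute change reads as a large proportional one.

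The inference about movement is what is at stake. Section 2 describes CES as reaching several root levels on both sides together, and describes remaining motor circuits in ALS as spastic and poorly coordinated. Co-activation is therefore plausible enough to be kept apart from help to the intended movement. Aim 2 also looks for the best CES parameters, and a ranking on this ratio could favour settings that mainly recruit muscles outside the task.

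**Working it through.** **The plan's own figures.** Aim 2 states no effect size, SD, alpha or power, so there is no statistical figure to reproduce. Its only arithmetic is scheduling, and it agrees: 24 × 2 = 48 sessions; 48 ÷ 1.5 = 32 weeks. It does not bear on this point.

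**Step 1: the ratio against baseline.** The documents give no EMG amplitudes, so every baseline *b* and added activity *d* below is an assumption. Linear addition gives (b + d)/b. Addition in quadrature, for activity unrelated to the ongoing signal, gives √(b² + d²)/b.

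| Pre-pulse RMS *b* | *d* = 5 µV, linear | *d* = 10 µV, linear | *d* = 10 µV, quadrature |
|---|---|---|---|
| 200 µV | 1.025 | 1.05 | 1.001 |
| 100 µV | 1.05 | 1.10 | 1.005 |
| 20 µV | 1.25 | 1.50 | 1.118 |
| 5 µV | 2.00 | 3.00 | 2.236 |

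The direction is the same in every column. The size is not: 10 µV on 100 µV is +10% or +0.5% according to how the signals add.

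If CES instead multiplies ongoing activity by a constant k, the ratio is (k × b)/b = k at every baseline, and quiet muscles are not inflated at all.

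**Step 2: pooling over tasks.** Take ECR with the same 5 µV linear rise throughout. Assume 200 µV when it drives wrist extension and 5 µV when it is quiet during opposition.

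- Extension alone: 205/200 = 1.025.
- Opposition alone: 10/5 = 2.00.
- Extension and opposition, equal weight: (1.025 + 2.00)/2 = 1.5125.
- Adding the combined task, with ECR again at 200 µV: (1.025 + 2.00 + 1.025)/3 = 1.35.

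In this example the ECR level reads +35% to +51%, while the rise in the task that ECR drives is 2.5%.

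**Step 3: averaging over muscles.** A CES-intensity main effect averages over muscle. Suppose the prime mover falls to 0.95, one antagonist reads 1.5 and the rest stay at 1.0.

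- 3 muscles: (0.95 + 1.5 + 1.0)/3 = 1.15.
- 4 muscles: (0.95 + 1.5 + 2.0)/4 = 1.11.
- 6 muscles: (0.95 + 1.5 + 4.0)/6 = 1.075.

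The average is above 1 although the prime mover fell. This applies only if the conclusion is drawn from the average; the plan defines no cross-muscle composite.

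**Step 4: silent period.** Aim 2 Outcomes sets the silence threshold from the muscle's own baseline mean plus 2 SD. A muscle with no volitional activity usually sits below its own threshold already and has nothing to suppress. A duration from such a muscle says nothing about inhibition, so it cannot inform Hypothesis 2.2.

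**The case against.** The other side has several good points.

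- **No any-muscle rule.** A reader might infer that a rise in any recorded muscle confirms Hypothesis 2.1. The documents state no such rule. The outcome is taken muscle by muscle, and the muscle factor allows results to be shown that way. The defect is that no target muscle or decision rule is named.
- **The sign is not wrong for the hypothesis.** A reader might infer that a rise in an antagonist is scored in the wrong direction. Hypothesis 2.1 concerns muscle activation, interpreted as corticospinal or motor neuron excitability. For that, a rise in FCR counts in the stated direction. The gap opens only when the result is read as facilitated movement.
- **Domination by quiet muscles is conditional.** Section 2 gives the goal of subthreshold CES as amplifying volitional signalling. If added activity scales with drive, Step 1 shows no inflation. Without a response, a quiet muscle's ratio also stays near 1.
- **The wording leans toward active muscles.** Aim 2 Data analysis speaks of ongoing voluntary contraction, section 3 words the hypothesis as wrist and hand, and the muscle list is optional, so FCR recording in Aim 2 is possible rather than certain.
- **This is a pilot** on mechanisms, safety and short-term biomarkers, with sham pulses mentioned.

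These points limit the claim but do not remove it. Sham controls for non-specific change; it does not separate help to the prime mover from CES-induced co-activation. Per-muscle display does not undo pooling over tasks. References to contraction do not set a baseline floor.

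**Conclusion.** The concern holds in a limited form. As written, the analysis pools a muscle's prime-mover, antagonist and resting data, and places no lower limit on the denominator of its ratio. It can therefore give a result that is sound as evidence of excitability but does not support the claim that the tested movement was facilitated. That second claim is what carries the step to an exercise study.

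The missing task factor, muscle-to-task assignment and baseline floor are matters of text and need no assumption. The size cannot be fixed from the documents. The figures of +2.5% against +100%, and the pooled +35% to +51%, assume baselines of 200 and 5 µV and an equal linear rise in both states. Under purely proportional facilitation the ratio inflation disappears, but pooling over a muscle's different roles remains. The documents do not support saying that quiet muscles will dominate the result, or that Hypothesis 2.1 would be confirmed by co-contraction. The prime-mover labels used here come from ordinary anatomy; the plan gives only segmental levels for the tasks.

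**What to change.** Before analysis:

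1. Add motor task, and its interaction with muscle, to the Aim 2 model.
2. For each task, prespecify the engaged prime mover(s) from muscles already on the list, for example ECR for wrist extension, APB for opposition and both for the combined task. Make sure these are recorded in every subject, and base the tests of Hypotheses 2.1 and 2.2 on those muscle-by-task cells.
3. Report antagonists (FCR in wrist extension) separately as co-activation, and other muscles descriptively as excitability data.
4. Form ratios and silent periods only where pre-pulse RMS is clearly above that muscle's resting level, with the margin fixed in advance. Resting EMG could be taken from the intervals of at least 10 seconds between trials.
5. Where the dynamometer or load cell is in use, report force beside EMG before concluding that movement was facilitated.

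The cost is mainly wording; no stimulation procedure changes. Fewer muscle cells contribute to the main test. The floor may also remove more trials from weak muscles at the lowest effort level, so excluded cells should be counted by group and effort.
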